23.6 Population AZD7442 Pharmacokinetic Data

A Phase I pharmacokinetic trial of AZD7442 was conducted in 48 healthy volunteers in the UK in August 2020. A Phase I, double-blind, placebo-controlled pK trial in 40 healthy Japanese volunteers is currently ongoing in Japan. The results of the UK study are not yet published.

23.7 Potential Benefits of AZD7442 Treatment in Immunosuppressed Patients Without Adequate COVID-19 RBD-IgG Antibody Protection

- AZD7442 reduces the risk of hospitalization or death when given to “at risk” patients as pre-exposure prophylaxis for prevention of SARS-CoV-2 infection. Infusion of this antibody mimics naturally produced antibodies generated by subjects infected with the SARS-CoV-2 virus. It is important to systematically evaluate whether use of AZD7442 for prevention of SARS-CoV-2 infection in immunosuppressed patients is protective against the SARS-CoV-2 virus in patients who have low or no antibody response to a COVID-19 vaccine or who, for a myriad of reasons, have not been adequately treated with a COVID-19 vaccine regimen. In patients treated with hematologic malignancy, active, significant immunosuppression is expected and as a result, there will be reduced protection against SARS-CoV-2 infection.
- This Real-World Evidence study will compare the incidence of symptomatic SARS-CoV-2 infection as well as SARS-CoV-2 related hospitalization and/or SARS-CoV-2 related death in all cancer patients treated with AZD7442 600 mg IM or IV. In addition, the study will compare Quality-of-Life metrics in all cancer patients treated with AZD7442 600 mg IM or IV as well as compare the same Quality-of-Life metrics between solid tumor and hematologic malignancy. To date, 300 mg IM has been tested as the dose for prevention while 600 mg IM has been tested as the dose for treatment post-infection, however, a recent FDA decision has requested that the dose of AZD7442 be increased to 600 mg for prevention.

24.0 REGULATORY OBLIGATIONS

24.1 Informed Consent

- An Informed Consent Form (ICF) will be prepared and approved by the IRB. The ICF will be signed digitally by all participants that can read or understand English at the time of enrollment. A paper version of the ICF may also be signed by a patient (1) if the site requires additional language that is only relevant for their site, (2) if it is needed for local regulatory requirements or (3) is in Spanish. Any updates to the ICF will be communicated to the PI at each study site. The ICF will be prepared in English.
- Before participation in the AISP, the site PI (oncologist) will be responsible for obtaining the digitally signed Informed Consent from the participant (or legally acceptable representative)

after adequate explanation of the aims, methods, anticipated benefits, and potential hazards of the program.

- The Informed Consent must be signed electronically and dated by the participant that can read or understand English (or caregiver/witness) and by the person who conducted the informed consent discussion. The digital ICF is retained perpetually in the participant's AISP digital record. (A hard copy of the Informed Consent Form may be provided to the participant (or caregiver/witness) upon request. If the patient only understands Spanish, they will sign the hard copy certified translation of the ICF. If a potential participant is either illiterate or legally blind and does not have a caregiver/witness who has agreed to assist the participant in his/her participation in the AISP, the participant is disqualified from program participation. If a participant is either illiterate or legally blind and has a caregiver/witness, both the participant and the caregiver/witness must electronically sign the ICF to attest that the Informed Consent was understood and that consent was freely given.

24.2 Authorization for Release of Health Information (including Prescriber Records, Pharmacy Records and Claim Information)

- All participants or their caregiver/witness will sign an Authorization for Release of Health Information Form (including Prescriber Records, Pharmacy Records and Medical Insurance Claims) that will be sent to the Prescriber, Pharmacy and Insurance Company that grants permission to release the participant's records to AISP.

24.3 Participant Confidentiality

- In order to comply with HIPAA, the oncologist must ensure that the participant's confidentiality is maintained. On documents submitted to the AISP or its designee, including medical record data, participants will be identified by use of a unique identification code that will be created at the time of participant's registration into the AISP. The participant's unique identification code will be printed on all hard-copy program related documents.

25.0 SAFETY REPORTING

25.1 Safety Overview

All safety events will be captured via Patient Experience/Clinical Outcome Assessment surveys. Safety data such as physical exams, labs and ECG data that are completed during the course of routine clinical care will be available to the MediMergent medical monitor through individual

patient EMR data. Safety events that occur as a result of an unplanned telehealth visit, non-routine office visit, ER/Urgent Care visit or hospitalization will be documented and all source documentation will be collected for review. PCR test results will be reported digitally from the testing lab to the site and the study site will report this result to MediMergent. For all Adverse Events or Serious Adverse Events, a separate data collection form, based on AstraZeneca guidelines, will be completed by the study site and submitted to MediMergent for data input and analysis. Reporting of Adverse Events and Serious Adverse Events will follow FDA Guidelines and AstraZeneca reporting procedures.

25.2 Reporting Guidelines

As this is an EUA pre-approval program, safety reporting guidelines for adverse events and serious adverse events are expected to be followed. In the event that a reportable safety event is identified for one or more patients, MediMergent will immediately notify AstraZeneca of such an event for their reporting purposes. The AISP will report all known safety events that would be reported in a pre-approval clinical trial on an annual basis unless otherwise requested by the FDA. Where expedited reporting is described, the sponsor will submit SUSARs to FDA within FDA required timelines for IND reports.

25.3 Expected SAEs

A program including 1,500 cancer patients followed for at least 12 months would be likely to encounter one or more of the following serious adverse events: sepsis, worsening of underlying cancer, respiratory failure, worsening of COPD, CHF, and death.

For purposes of this study, all hospitalizations and/or deaths will be considered a SAE.

Hospitalization for a pre-existing condition that has not worsened (i.e., change a pacemaker battery) or for elective surgery will NOT be considered a SAE unless the hospitalization is prolonged by complications. These events will be collected and reported as SAEs only if the event is more severe than expected for the participant's current clinical status and medical history or if the Investigator feels that it is related to study drug. These will be collected and reported as SAEs as delineated below. Since it will not be possible to delineate in a single participant whether the hospitalization is directly related to SARS-CoV-2 complications, their underlying cancer or treatment for this cancer or could be related to AZD7442 causing more severe disease due to ADE, all hospitalizations for management of acute illness, regardless of cause, will be sent for evaluation by the Clinical Events Committee.

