25.13.5 Deaths

- All deaths will be SAEs and will require completion of the SAE Report Form. This form includes questions regarding cardiovascular (including sudden cardiac death) and non-cardiovascular death.
- The Death related SAE form should be completed after the occurrence or outcome of death is reported. Initial and follow-up reports regarding death must be completed within one week of when the death is reported.

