25.13.6 Investigator Responsibility

To satisfy regulatory requirements, all SAEs that occur during the study (including the protocol-defined follow-up period) regardless of judged relationship to treatment with study product must be reported to MediMergent by the investigator within 24-hours of when the investigator learns about it or, if the event occurs on a weekend or national holiday, on the next working day. The following information should be provided to record the event accurately and completely:

- study name or number
- investigator and study site identification
- patient number
- patient initials
- name of SAE(s)
- investigator's assessment of the relationship of the SAE to the study drug (no reasonable possibility or reasonable possibility)
- Additional information may include the following:
 - age and gender of patient
 - date of study drug administration

- date and amount of administered dose of study product
- onset date and end date of SAE
- description of clinical course of SAE
- action taken
- outcome if known
- severity
- concomitant therapy (including doses, routes, and regimens) and treatment of the event
- pertinent laboratory test data, or other diagnostic test data
- medical history
- if the adverse event results in death
 - cause of death (whether or not the death was related to study product)
 - autopsy findings (if available).

The investigator must ensure that the IRB is also informed of the event in accordance with local regulations.

Note: Although pregnancy is not a SAE, the process for reporting a pregnancy is the same as that for reporting a SAE but using the pregnancy form.

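### Sections 25.3 and 18.5 make SAE reporting conditional for events they do not name, and on either reading the condition conflicts with other protocol text

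*Protocol*

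**What the plan says.** Section 25.3 opens with a list of serious events likely in this population: sepsis, worsening cancer, respiratory failure, worsening COPD, CHF and death. Its second paragraph then makes these statements in order:

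1. General rule: "For purposes of this study, all hospitalizations and/or deaths will be considered a SAE".
2. Exception: admission for a pre-existing condition that has not worsened, or for elective surgery, "will NOT be considered a SAE unless the hospitalization is prolonged by complications".
3. Filter: "These events will be collected and reported as SAEs only if the event is more severe than expected" given the participant's clinical status and history, "or if the Investigator feels that it is related to study drug".
4. An unconditional sentence saying that these (again with no noun) will be reported as SAEs as set out below.
5. A statement that "it will not be possible to delineate in a single participant whether the hospitalization is directly related to SARS-CoV-2 complications", to the cancer or its treatment, or to AZD7442 through ADE. For that reason all acute-illness hospitalizations go to the Clinical Events Committee (CEC).

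Section 18.5 repeats this almost word for word. Its exception differs: the stay must be prolonged by complications of related SARS-CoV-2 therapy, whereas 25.3 accepts any complications.

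The reporting duties elsewhere carry no such filter. Section 25.13.5 says: "All deaths will be SAEs and will require completion of the SAE Report Form". Section 25.13.6 says that all SAEs "regardless of judged relationship to treatment with study product must be reported", within 24 hours. Section 25.8 also requires all SAEs within 24 hours.

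**The concern.** A site coordinator has to decide from this paragraph whether an admission needs an SAE form. The conditional sentence does not say which events it governs, and the sentence after it drops the condition. Two careful sites could reach opposite answers for the same event.

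All patients receive AZD7442 (section 5.1), so no concurrent control arm would show up uneven capture. Up to 75 sites are planned (section 6.1). CHF is on the 25.3 list and is also an event of special interest in 25.15, and 25.3 itself raises ADE as a possible cause of hospitalization. If some sites hold back acute admissions that look ordinary for a cancer patient and others report them all, SAE counts will be too low and will not mean the same thing from site to site.

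**Working it through.** No arithmetic applies, because the protocol states no SAE or hospitalization rate. The check is to take each possible meaning of the unnamed events and follow it through the other sections.

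**Narrow reading: the exempted admissions only.** This is the most natural reading by position, since the filter directly follows the exception. Take a planned admission for an unchanged condition that is prolonged by an ordinary surgical complication, judged within expectation and unrelated to the drug:

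- Exception in 25.3 (prolonged by complications): SAE.
- Exception in 18.5 (prolonged by complications of related SARS-CoV-2 therapy): not an SAE.
- Filter in 25.3 and 18.5 (exceeds expectation or drug-related): not an SAE.
- Section 25.13.1: scheduled admissions of this kind are not SAEs, yet the same bullet calls a complication that prolongs a stay serious. This agrees with 25.3 on prolongation, but not with the 18.5 wording or the filter.

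These rules cannot all be followed.

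**Broad reading: acute hospitalizations, or the listed expected SAEs.** Take an unplanned admission for decompensated CHF, judged in line with the patient's history and unrelated to the drug:

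- General rule in 25.3 and 18.5: SAE.
- Filter: not reported as an SAE.
- Section 25.13.1: inpatient hospitalization for an adverse event is serious, with no test of expectedness or relationship. Section 25.13.2 counts any formal inpatient admission.
- Sections 25.8 and 25.13.6: all SAEs reported, the latter whatever the judged relationship.

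Here the filter contradicts the rule two sentences above it and the later sections. For deaths it also contradicts 25.13.5.

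**Is the broad reading realistic?** The protocol uses the same kind of test for disease events elsewhere. Section 25.7.3 excludes expected disease progression unless it exceeds expectation. Section 25.14 applies a greater-than-expected-or-related test to COVID-19 progression, up to respiratory failure with invasive ventilation. A site that reads 25.3 beside these has textual support for filtering acute events.

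**Does CEC referral close the gap?** Sections 20.1 and 25.22 give the CEC adjudication of SARS-CoV-2 events, their relatedness and their severity. Referral does not generate the 24-hour report in 25.8 and 25.13.6, or an entry in the safety database of 25.23.

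**The case against.** The best case against is that this is a drafting slip with little practical reach. The filter follows the elective and pre-existing exception directly and most naturally qualifies it. In 18.5 the list of likely SAEs sits in a separate section (18.4), so it can hardly be the antecedent there. On that reading only planned admissions are affected. Sections 25.13.1, 25.13.2, 25.13.5 and 25.13.6 state the duty plainly, 18.6 and 25.4 require hospitalizations and deaths on the Safety Report Form, and acute admissions reach the CEC. A site reading the whole protocol could not properly omit a CHF or respiratory-failure admission.

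Much of this stands. The narrow reading is the likelier one, and deaths are well protected by 25.13.5. Two things remain. The narrow reading still leaves incompatible triggers. And the duties in 25.8 and 25.13.6 attach to SAEs, so they do not help once a site has used 25.3 to decide that an event is not reportable as one.

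A reader might also infer that the whole filter rests on a judgement the protocol itself calls impossible. The text does not support that. The sentence concerns only the cause of a hospitalization. It says nothing of deaths or of severity against expectation, and because the two limbs are joined by an or, the severity limb can trigger reporting by itself. There is tension with the relatedness limb for hospitalizations, and with 25.7.7, which requires a causality assessment for every event, but no more than that.

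**Conclusion.** The point holds as an inconsistency in a safety-reporting rule. The sentence in 25.3 and 18.5 has no named subject, is followed by an unconditional one, and conflicts with other text on both readings. The narrow reading affects planned admissions only. The broad reading, less natural but plausible, exposes acute hospitalizations to under-reporting.

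No size can be given. It is tempting to apply the 4.0% mortality cited in 23.1 for cancer patients without COVID-19 to the 1,500 participants and assume that most of those deaths would be filtered out. The documents do not support this. That figure has no stated follow-up period, this trial excludes ECOG 2 or higher and expected survival under 12 months, the share a site would filter is unknown, and deaths are the category that 25.13.5 protects most clearly. Nor do the documents give a reason to expect misreading to differ between treatment strata. The practical risk rests on one assumption: that at least some sites act on 25.3 or 18.5 without reconciling it with 25.13.

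**What to change.** In both 25.3 and 18.5:

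- Delete the conditional sentence, or replace its subject with the events meant: planned admissions for an unchanged pre-existing condition or for elective surgery.
- Use one exception for those admissions, worded the same in 18.5, 25.3 and 25.13.1.
- State that all other hospitalizations and all deaths are reported as SAEs regardless of expectedness or judged relationship, in line with 25.13.5 and 25.13.6.
- State that expectedness (defined in 25.13.3) is used only for the expedited-reporting decision in 25.9.

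The cost is two sentences in the protocol, a memo to sites, and possibly a few more SAE forms where a site had applied the filter broadly.

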25.4 Investigator Responsibility

The Investigator and any qualified designees are responsible for detecting, documenting, and reporting events that meet the definition of an AE or SAE and remain responsible for following up AEs that are serious, considered related to the study intervention or the study, or that caused the participant to discontinue the study. Data on hospitalization or death should additionally be recorded on the Safety Report Form, for all relevant sections.

25.5 Recording, Evaluating and Assessing Causality

The method of recording, evaluating, and assessing causality of AEs and SAEs and the procedures for completing and transmitting SAE reports are provided in this document.

25.6 ASSESSMENT OF SAFETY

In this study, safety will be assessed by evaluating adverse events, chest x-rays, bacterial cultures and COVID-19 PCR and genomic test results. In addition, important infectious and oncologic safety events will be reviewed from CEC-adjudicated data for SARS-CoV-2 infection, hospitalization and death.

The MediMergent Pharmacovigilance team will be responsible for oversight of all safety data and for determining the expectedness of all SAEs, expedited reporting of individual cases, and safety updates to regulatory authorities and AstraZeneca.

25.7 ADVERSE EVENTS

25.7.1 Definition of an Adverse Event

- An adverse event is any untoward medical occurrence in a patient that develops or worsens in severity during the conduct of a clinical study of a pharmaceutical product and does not necessarily have a causal relationship to study product.
- In this study, any adverse event occurring after the patient has signed the informed consent document and received AZD7442 administration should be processed and reported as an adverse event. An adverse event can be any unfavorable and unintended physical sign, symptom, or laboratory parameter that develops or worsens in severity during the course of the study, or significant worsening of the disease under study or any concurrent disease, whether or not considered related to study product. Stable chronic conditions (such as nausea) that are present prior to study entry and do not worsen during the study will not be considered adverse events. Accordingly, an adverse event could include any of the following:

- intercurrent illnesses
 - physical injuries
 - events possibly related to concomitant medication
 - significant worsening (change in nature, severity, or frequency) of the disease under study or other pre-existing conditions.
 - drug interactions
 - laboratory or diagnostic test abnormalities occurring after the start of the study that result in the withdrawal of the patient from the study, requires medical treatment or further diagnostic work-up, or is considered by the study investigator to be clinically significant.
- Note:** Abnormal laboratory test results during the screening period that preclude a patient from entering the study or from receiving study treatment are not considered adverse events.

- An unsolicited adverse event is an adverse event that is communicated by a participant who has signed the informed consent. Unsolicited AEs include serious and non-serious AEs. Potential unsolicited AEs may be medically attended (i.e., symptoms or illnesses requiring a hospitalization, or emergency room visit, or visit to/by a health care provider). The participants will be instructed to contact the site as soon as possible to report medically attended event(s), as well as any events that, though not medically attended, are of participant concern. Detailed information about reported unsolicited AEs will be collected by qualified site personnel and documented in the participant's records. Unsolicited AEs that are not medically attended nor perceived as a concern by participant will be collected following completion of the follow-up Patient Experience/COA survey by the participant and review of available medical records.
- Solicited AEs are predefined such as injection site reactions and systemic events for which the participant is specifically questioned in the follow-up Patient Experience/COA survey.

25.7.2 Events that Meet the AE Definition

- Any event that occurred in the first 24 hours post AZD7442 administration
- Symptoms of SARS-CoV-2 infection
- Positive PCR-RT SARS-COV-2 test
- Any unplanned telehealth visit
- Any non-routine office visit

- Any ER/Urgent Care visit
- Signs, symptoms, or the clinical sequelae occurring in the first 24 hours post administration
- If the Investigator considers that there was a causal relationship between treatment with AZD7442 or protocol design/procedures and a patient's underlying disease progression, then this must be reported as an AE or SAE.
- Signs, symptoms, or the clinical sequelae of a suspected overdose of either study intervention or a concomitant medication. Overdose per se will be reported as an AE/SAE even if it was not associated with AE/SAE. Intentional drug overdose with possible suicidal/self-harming intent will be reported as an AE/SAE. Such overdoses will be reported regardless of sequelae.
- "Lack of efficacy" or "failure of expected pharmacological action" per se will not be reported as an AE or SAE. Such instances will be captured in the efficacy assessments. However, the signs, symptoms, and/or clinical sequelae resulting from lack of efficacy will be reported as AE or SAE if they fulfill the definition of an AE or SAE.

25.7.3 Events that do NOT Meeting the AE Definition

- Any clinically significant abnormal laboratory findings or other abnormal safety assessments which are associated with the underlying disease, unless judged by the investigator to be more severe than expected for the participant's condition.
- Elective treatment of a pre-existing condition that did not worsen from baseline.
- The disease/disorder being studied or expected progression, signs, or symptoms of the disease/disorder being studied, unless more severe than expected for the participant's condition.
- Medical or surgical procedure (e.g., endoscopy, appendectomy): the condition that leads to the procedure is the AE.
- Situations in which an untoward medical occurrence did not occur (social and/or convenience admission to a hospital).
- Anticipated day-to-day fluctuations of pre-existing disease(s) or condition(s) present or detected at the start of the study that do not worsen.

